#### **Clinical Laboratory Tests**

Laboratory data will be summarized by treatment arm and type of test. Descriptive statistics will be calculated for each laboratory analyte for observed values and changes from baseline at each scheduled time point. Graphical presentation of changes in laboratory parameters can be made as applicable. Abnormalities will be determined according to the DAIDS grading table (see Attachment 2) and in accordance with the normal ranges of the clinical laboratory. Maximum toxicity grade after baseline will be tabulated and special attention will be given to the subjects who develop grade 3 or 4 toxicities.

#### Serum Creatinine and Cystatin C

The changes from baseline in serum creatinine, eGFRcr (by Cockcroft-Gault and by CKD-EPI) and eGFRcyst (by CKD-EPI) at Weeks 24, 48, and 96 will be summarized by treatment arm and using descriptive statistics. The difference between the 2 treatment arms in change from baseline in serum creatinine and eGFR at Weeks 24 and 48 will be tested using ANCOVA, including corresponding baseline value and other clinically relevant factors (if deemed necessary) in the model. A supportive repeated measures analysis will be performed to obtain an estimate of the between-treatment difference along with its 95% CI at Weeks 24 and 48. This model will include post-baseline change from baseline as a response variable, terms for treatment, visit, the interaction of visit and treatment and the corresponding baseline value as a covariate and other clinically relevant factors (if deemed necessary). An unstructured covariance matrix will be used to model the correlation among repeated measurements.

#### **Renal Biomarkers**

Selected renal biomarkers, including RBP and beta-2-microglobulin, will be summarized by treatment arm and visit using descriptive statistics. The comparison between the 2 treatment arms at Weeks 24 and 48 will be performed using the Van Elteren test stratified for bPI used at screening. The within-treatment comparison will be performed using Wilcoxon signed-rank test.

# Vital Signs

Descriptive statistics of vital sign (pulse rate, systolic and diastolic blood pressure) values and changes from baseline will be summarized at each scheduled time point. The percentage of subjects with values beyond clinically important limits will be tabulated. For definitions of abnormalities of vital signs, refer to Attachment 6.

#### Physical examination

Physical examination findings and changes from baseline at each scheduled time point will be summarized.

#### **Bone investigations**

Baseline, post-baseline, and the percent change from baseline at Weeks 24, 48, and 96 for selected bone biomarkers, including CTX, P1NP, PTH, and 25-hydroxy vitamin D, will be summarized by treatment arm and visit using descriptive statistics. The within-treatment comparison will be done using Wilcoxon signed-rank test. The comparison between the 2 treatment arms will be performed using the Van Elteren test stratified for bPI used at screening.

The percent change from baseline at Weeks 24, 48, and 96 in spine and hip BMD as well as the change from baseline in BMD T-score will be summarized by treatment arm and visit using descriptive statistics. The between-treatment differences at Weeks 24 and 48 will be estimated using ANCOVA model, including baseline BMD value and other clinically relevant factors (if deemed necessary) in the model. The within-treatment comparison will be done using paired t-test. A supportive longitudinal repeated measures analysis will be performed on this endpoint to obtain an estimate of the between-treatment difference along with its 95% CI at Weeks 24 and 48. This model will include post-baseline percent change from baseline as a response variable, terms for treatment, visit, the interaction of visit and treatment and the corresponding baseline BMD value as a covariate and other clinically relevant factors (if deemed necessary). An unstructured covariance matrix will be used to model the correlation among repeated measurements.

The BMD T-score will be summarized descriptively. BMD status based on the T-score (normal:  $\geq$ -1; osteopenia: from <-1 to -2.5; osteoporosis: <-2.5) will be tabulated.

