### Safety

- The original terms used by investigators to identify AEs will be coded using the Medical Dictionary for Regulatory Activities (MedDRA). All reported AEs with onset during the study will be included in the analysis. For each AE, the percentage of subjects who experience at least 1 occurrence of the given event will be summarized.

Summaries (number and percentage of subjects) of treatment-emergent AEs (by system organ class and preferred term) will be provided by treatment arm. Additional summaries will include summaries for AEs by severity grade (with special attention to grade 3 or 4 AEs), investigator's assessment of relationship to treatment, SAEs, and AEs leading to discontinuation of study treatment.

- The changes from baseline in serum creatinine, eGFRcr (by Cockcroft-Gault and by CKD-EPI) and eGFRcyst (by CKD-EPI) at Weeks 24, 48, and 96 will be summarized by treatment arm and using descriptive statistics. The difference between the 2 treatment arms in change from baseline in serum creatinine and eGFR at Weeks 24 and 48 will be tested using analysis of covariance (ANCOVA),

including corresponding baseline value and other clinically relevant factors (if deemed necessary) in the model.

Only in subjects participating in the bone investigation substudy at selected study sites:

- The percent change from baseline at Weeks 24, 48, and 96 for selected bone biomarkers will be summarized by treatment arm and visit using descriptive statistics. The within-treatment comparison will be done using Wilcoxon signed-rank test. The comparison between the 2 treatment arms will be performed using the Van Elteren test stratified for bPI used at screening.
- The percent change from baseline at Weeks 24, 48, and 96 in spine and hip BMD as well as the change from baseline in BMD T-score will be summarized by treatment arm and visit using descriptive statistics. The between-treatment differences at Weeks 24 and 48 will be estimated using ANCOVA model, including baseline BMD value and other clinically relevant factors (if deemed necessary) in the model. The within-treatment comparison will be done using paired t-test.

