#### Secondary Objectives

The secondary objectives of this study are:

- To evaluate superiority of switching to a D/C/F/TAF once-daily single-tablet regimen versus continuing the current bPI combined with FTC/TDF in regard to the proportion of virologic rebounders, in case noninferiority is established;
- To evaluate the proportion of rebounders through Week 24 in the 2 treatment arms;
- To evaluate efficacy as determined by continued suppression of HIV-1 RNA (<20, <50, and <200 HIV-1 RNA copies/mL as defined by the FDA snapshot analysis and time to loss of virologic response [TLOVR] algorithm) at Weeks 24 and 48 in the 2 treatment arms;
- To evaluate the safety and tolerability of the D/C/F/TAF regimen through 24 and 48 weeks of treatment;
- To evaluate the change from baseline in serum creatinine, eGFR for creatinine clearance (eGFRcr, by Cockcroft-Gault and by Chronic Kidney Disease Epidemiology Collaboration [CKD-EPI]) and eGFR for cystatin C clearance (eGFRcyst, by CKD-EPI) in the 2 treatment arms at Weeks 24 and 48;
- To evaluate the change from baseline in renal biomarkers at Weeks 24 and 48;
- To evaluate immunologic changes (CD4+ cell count) through 24 and 48 weeks of treatment in the 2 treatment arms;
- To evaluate adherence to drug intake (as derived by drug accountability data), and explore correlation with primary efficacy outcome;
- To evaluate resistance in subjects who show confirmed virologic rebound through Weeks 24 and 48 in the 2 treatment arms;
- To evaluate long-term efficacy, resistance, and safety of the D/C/F/TAF regimen (until Week 96 and beyond);
- To evaluate the steady-state pharmacokinetics of DRV in the D/C/F/TAF arm.

Secondary objectives to be assessed in a bone investigation substudy performed at selected study sites:

- To evaluate the changes from baseline in bone biomarker levels at Weeks 24 and 48;
- To evaluate the safety of the 2 treatment arms as determined by the percent change from baseline in spine and hip bone mineral density (BMD) and changes in associated T-score at Weeks 24 and 48.

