# 11.1.2. Secondary Endpoints

Secondary endpoints in this study are:

- The proportion of subjects having confirmed virologic rebound through 24 and 96 weeks of treatment;
- The time to virologic rebound in weeks;
- The proportion of subjects experiencing grade 3 and 4 AEs through 24, 48, and 96 weeks of treatment;
- The proportion of subjects experiencing SAEs and premature discontinuations due to AEs through 24, 48, and 96 weeks of treatment;
- The change from baseline in serum creatinine, eGFRcr (by Cockcroft-Gault and by CKD-EPI) and eGFRcyst (by CKD-EPI) at Weeks 24, 48, and 96;
- The change from baseline in renal biomarkers at Weeks 24, 48, and 96;

- Clinical Protocol TMC114IFD3013 Amendment 4
- The proportion of subjects with HIV-1 RNA <20, <50, and <200 copies/mL at Weeks 24, 48, and 96 as defined by the FDA snapshot analysis and TLOVR algorithm;
- The change from baseline in CD4+ cell count at Weeks 24, 48, and 96;
- Adherence to drug intake based on drug accountability through 24, 48, and 96 weeks;
- Genotypic, and phenotypic if applicable, resistance to ARVs in the 2 treatment arms in subjects with confirmed HIV-1 RNA rebound through Weeks 24, 48, and 96;
- Pharmacokinetic parameters for DRV in the D/C/F/TAF arm.

Secondary endpoints to be assessed in subjects participating in a bone investigation substudy at selected study sites:

- The percent change from baseline in bone biomarkers CTX, P1NP, PTH, and 25-hydroxy vitamin D at Weeks 24, 48, and 96.
- The percent change from baseline in spine and hip BMD and change from baseline in BMD T-score at Weeks 24, 48, and 96.

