#### Rebound Rates (Snapshota or Confirmed ≥50 Copies/mL) From Historical Studies of Table 5:

ART=antiretroviral therapy; VF=virologic failure; f/bPI=from boosted PI

a HIV-1 RNA ≥50 copies/mL through 48 weeks or discontinuation due to lack of efficacy or discontinuations due t other reasons and last HIV-1 RNA  $\geq$ 50 copies/mL.

b Efficacy analysis performed after at least 6 months HIV-1 RNA <50 copies/mL.

For the bone investigation substudy, with 300 subjects (200 in the D/C/F/TAF treatment arm versus 100 in the control arm) and assuming an inter-subject variability of 4%, there is approximately 98% power to detect a 2% difference between the D/C/F/TAF treatment arm and the control arm in percent change from baseline in BMD at the spine. Other power calculations are presented in Table 6.

Table 6:	BMD at the L	umbar S	Spine, Pow	er Calcu	lations
		3.6		0	G

DMD 44b I and Got D

	Mean % Change from Baseline	Common Standard Deviation (%)	Power
	2	3.5	>99%
N=300	2	4	98%
IN-300	2	3.5	>99%
	5	4	>99%

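### The within-arm signed-rank test for bone biomarkers names no variable; applied to percent change, its natural reading, it leans toward declaring increases

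*Protocol*

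**What the plan says.** Protocol 11.1.2 defines the endpoint: "The percent change from baseline in bone biomarkers CTX, P1NP, PTH, and 25-hydroxy vitamin D at Weeks 24, 48, and 96". Protocol 11.6 (Bone investigations) opens by summarising "Baseline, post-baseline, and the percent change from baseline at Weeks 24, 48, and 96 for selected bone biomarkers" and then says "The within-treatment comparison will be done using Wilcoxon signed-rank test". The synopsis is narrower. It says "The percent change from baseline at Weeks 24, 48, and 96 for selected bone biomarkers will be summarized by treatment arm and visit", with the signed-rank sentence almost immediately after it. Neither place names the tested variable, a transformation or a significance level.

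For the comparison between arms, 11.6 says "The comparison between the 2 treatment arms will be performed using the Van Elteren test stratified for bPI used at screening". The objective in Protocol 2.1 names no scale: "To evaluate the changes from baseline in bone biomarker levels at Weeks 24 and 48". Protocol 11.2 plans the substudy as "200 in the D/C/F/TAF treatment arm versus 100 in the control arm".

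The supplied SAP covers the Week 96 analysis only. Its section 5.7.2 gives bone biomarkers descriptive statistics, and its signed-rank sentence stands under the DXA scan heading.

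**The concern.** The signed-rank test asks whether the tested quantity is symmetric about zero. If a marker does not change, baseline and follow-up values can be swapped without altering their joint distribution. The raw difference and the log ratio then merely change sign, so both are symmetric about zero. Percent change is not: swapping turns +p into -p/(1+p), which is always smaller in size. Increases therefore receive larger ranks than the decreases that mirror them, although the median percent change is zero.

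The direction matters here. Protocol 1.5.4 reports that TAF monofumarate in rats appeared to raise markers of bone turnover and lower 25-hydroxyvitamin D. A test that leans upward can imitate the rise in turnover, through CTX and P1NP, and it has less power to show the fall in vitamin D. It also has less power to show a fall in turnover after TDF is stopped.

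**Working it through.** **The plan's own figure.** The only power stated for the substudy concerns spine BMD: 98% for a 2% difference, SD 4%, 200 against 100 subjects. The noncentrality is 2/(4 × √(1/100 + 1/200)) = 2/(4 × 0.1225) = 4.08, and Φ(4.08 − 1.96) = Φ(2.12) = 98.3%. It reproduces, but it gives no information on biomarker variability.

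**Inputs for the check.** Arm sizes of 200 and 100 come from Protocol 11.2. The SD of log(post/baseline), called s, is not in the documents and is varied from 0.1 to 0.6. A two-sided 5% level is assumed.

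**Model.** Baseline = exp(m + e1) and follow-up = exp(m + e2 + μ). The subject term m has SD 0.5, and e1 and e2 each have SD s/√2. With μ = 0 the two visits are exchangeable. Each setting has 20,000 simulated trials and uses the normal-approximation signed-rank test, rejecting beyond ±1.96. The Monte Carlo standard error near 25% is √(0.25 × 0.75/20,000) = 0.3 percentage points.

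**No true change, test on percent change** (nominal 2.5% each way, 5% in total):

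| s | n=100 increase / decrease | total | n=200 increase / decrease | total |
|---|---|---|---|---|
| 0.1 | 4.0% / 1.4% | 5.3% | 5.1% / 1.0% | 6.2% |
| 0.2 | 7.0% / 0.8% | 7.8% | 10.1% / 0.5% | 10.6% |
| 0.3 | 10.3% / 0.5% | 10.8% | 16.0% / 0.2% | 16.2% |
| 0.4 | 14.3% / 0.3% | 14.5% | 24.9% / 0.1% | 25.0% |
| 0.5 | 19.4% / 0.2% | 19.6% | 33.7% / 0.0% | 33.7% |
| 0.6 | 24.2% / 0.1% | 24.3% | 43.4% / 0.0% | 43.4% |

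(Totals were rounded separately.) On raw change or log ratio, the same data give 2.2% to 2.8% in each direction in every row.

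**Analytic check.** For small s, the probability that two percent changes sum to more than zero is about 0.5 + 0.141s, so the expected shift in the test statistic is about 0.141 × s × √(3n). At s = 0.2 and n = 200 this is 0.141 × 0.2 × 24.5 = 0.69, and Φ(0.69 − 1.96) = 10.2%, against 10.1% simulated. At s = 0.2 and n = 100 it is 0.141 × 0.2 × 17.3 = 0.49, and Φ(0.49 − 1.96) = 7.1%, against 7.0%. The shift grows with √n, which is why the larger arm is affected more.

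**Power for a true 10% fall in the median ratio:**

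| s | n=100 log ratio | n=100 percent change | n=200 log ratio | n=200 percent change |
|---|---|---|---|---|
| 0.2 | 100.0% | 99.6% | 100.0% | 100.0% |
| 0.3 | 92.5% | 75.7% | 99.8% | 96.4% |
| 0.4 | 71.8% | 35.9% | 95.3% | 62.3% |
| 0.5 | 53.3% | 15.4% | 82.8% | 25.6% |

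At n = 200 and s = 0.4, raw change gives 93.1%. A 5% fall at n = 200 and s = 0.4 is found 6.9% of the time on percent change, against 41.9% on the log ratio. A 20% fall at n = 200 is found at least 99% of the time on either scale for s up to 0.5.

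**Between arms.** Percent change is a strictly increasing function of the log ratio, so subjects have the same ranks within each stratum and the Van Elteren result is identical on either scale.

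**The case against.** **The tested variable is inferred.** The signed-rank sentence names none. Section 11.6 lists baseline and post-baseline values as well as percent change, so a paired test of the raw values would fit its words and would hold its level. The same test is named for renal biomarkers, whose endpoint is plain change. Protocol section 11 is a general description that leaves details to the SAP, and no SAP for Week 24 or Week 48 is among the documents. All of this stands: a reader might infer that the protocol prescribes the test on percent change, and it does not say so. Still, percent change is the defined endpoint and the only change measure named beside the test, so it is the reading a programmer would most likely follow.

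**The size rests on an assumed SD.** This also stands. A reader might infer that the test generally reports false increases and hides true decreases. The figures do not support that: at s = 0.1 the excess error is about one percentage point or less, and a 10% fall at s = 0.2 is found almost always.

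**Whether an increase is false depends on the estimand.** Under the lognormal model with median ratio 1, mean percent change is exp(s²/2) − 1, which is exp(0.08) − 1 = 8.3% at s = 0.4, so the mean of the defined endpoint is above zero. That is true, but the signed-rank test does not estimate this mean. Expressing baseline as a percent change from follow-up would give the same +8.3%, so it cannot be evidence of a rise over time.

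**The consequences are limited.** A reader might infer that the bone comparison with TDF is compromised. It is not: that comparison rests on the Van Elteren test and the BMD ANCOVA. Nor is any comparison of the two within-arm p-values planned, and with 200 and 100 subjects their power would differ on any scale.

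**Conclusion.** The point holds as a conditional one. If the within-arm signed-rank test is run on percent change, it tests symmetry of percent change rather than absence of change, and it errs upward. The direction follows from exchangeability of positive values and needs no distributional model. The size does need one: the figures assume lognormal values, a two-sided 5% level and a log-ratio SD that the documents do not supply. The effect is slight at an SD of 0.1 and material from about 0.2 upward, and it is larger in the 200-subject arm. It concerns a secondary, within-arm safety test in a substudy, at Weeks 24 and 48. The protocol also lists Week 96, but the Week 96 SAP does not test biomarkers, so the concern should not be extended to that analysis.

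**What to change.** In Protocol 11.6 and the synopsis, state that the within-arm signed-rank test for CTX, P1NP, PTH and 25-hydroxy vitamin D is applied to log(post/baseline). Report the back-transformed estimate, a ratio to baseline, with its 95% CI. Keep percent change for the descriptive tables. Raw change would also hold its level. The log ratio is preferable because it had slightly more power for decreases here and gives the same between-arm ranks as percent change.

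The cost is one sentence in each place and one changed input variable in the program, with no new data. SAP 1.2 describes the Week 24 and Week 48 analyses as already done, so any within-arm biomarker p-values produced on percent change should be re-run on the log ratio and reported that way.

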#### 11.7. Pharmacokinetic Analyses

Individual pharmacokinetic parameters will be derived with population pharmacokinetic analysis (if appropriate population pharmacokinetic models are available) using the sparse samples collected at Weeks 2, 4, 8, 12, 24, 36, and 48, or ESTD (if applicable) for DRV, and other ARVs as requested by the sponsor. Model specifications will be described in separate report(s), as applicable.

Descriptive statistics will be calculated for the plasma concentrations of DRV by visit and for the derived pharmacokinetic parameters as available, and also for any of the ARVs analyzed upon sponsor's request (COBI, FTC, TAF, TFV, ARVs in the control arm), if applicable. Summary

statistics include n, mean, SD, coefficient of variation (CV), geometric mean, median, minimum and maximum.

#### 11.8. Treatment Adherence

Treatment adherence based on pill count will be summarized by means of descriptive statistics and frequency tabulations.

# 11.9. Data Monitoring Committee

An external DMC will be established to monitor the safety and efficacy information to ensure the safety of the subjects enrolled in this study, and to allow regular assessment of the risk/benefit profile of the applied therapy schemes. The details will be provided in a separate DMC charter.

A formal futility analysis for lack of (non-inferior) efficacy of the D/C/F/TAF regimen will be performed, using a conditional power approach, ie, probability of claiming non-inferiority at the completion of the study based on the available interim data. To this end, available interim data regarding virologic rebound will be used. Further details regarding the derivation of the conditional power and the choice of threshold for the conditional power to stop for futility will be provided in the DMC charter and DMC statistical analysis plan. The futility analysis will be guided by the DMC, and the sponsor and study team will remain blinded. It is not the intention to stop the study early in case of noninferiority/superiority of the D/C/F/TAF regimen versus the control group.

In addition, a blinded sample size re-estimation procedure will be applied to allow for an adjustment in sample size to maintain adequate power in case the overall rate of rebound is anticipated to be different than assumed. Details will be provided in the DMC charter.

The DMC will consist of 2 external medical experts in the relevant therapeutic area and 1 external statistician. The DMC responsibilities, authorities, and procedures will be documented in its charter.

#### 12. ADVERSE EVENT REPORTING

Timely, accurate, and complete reporting and analysis of safety information from clinical studies are crucial for the protection of subjects, investigators, and the sponsor, and are mandated by regulatory agencies worldwide. The sponsor has established Standard Operating Procedures in conformity with regulatory requirements worldwide to ensure appropriate reporting of safety information; all clinical studies conducted by the sponsor or its affiliates will be conducted in accordance with those procedures.

#### 12.1. Definitions

# 12.1.1. Adverse Event Definitions and Classifications

#### Adverse Event

An AE is any untoward medical occurrence in a clinical study subject administered a medicinal (investigational or noninvestigational) product. An AE does not necessarily have a causal relationship with the treatment. An AE can therefore be any unfavorable and unintended sign (including an abnormal finding), symptom, or disease temporally associated with the use of a medicinal (investigational or noninvestigational) product, whether or not related to that medicinal (investigational or noninvestigational) product. (Definition per ICH)

This includes any occurrence that is new in onset, or aggravated in severity or frequency, or changed in nature from the baseline condition, abnormal results of protocol-mandated diagnostic procedures including laboratory test abnormalities (eg, venipuncture, biopsy), and complications and termination of pregnancy.

AE collecting starts with the signing of the ICF (see Section 12.4.1 for time of last AE recording).

An AE does not include the following (see also Section 12.3 and 12.4.3):

- Medical or surgical procedures if the condition that leads to the procedure is an AE
- Pre-existing diseases or conditions or laboratory abnormalities present or detected before the screening visit that do not worsen; any medical condition or clinically significant laboratory abnormality with an onset date before the ICF is signed, is not an AE. It is considered to be pre-existing and should be documented in the medical history eCRF.
- Situations where no untoward medical occurrence has occurred (eg, hospitalization for elective surgery, social and/or convenience admissions)
- Overdose without clinical sequelae
- Uncomplicated pregnancy
- An induced elective abortion to terminate a pregnancy without medical reason

